## PROTOCOL SYNOPSIS

Protocol Title:	Clarification of Abatacept Effects in SLE with Integrated Biologic and Clinical Approaches (The ABC Study) The ABC Study:
Site Numbers/ Names:	Site 1: Oklahoma Medical Research Foundation
Research Hypothesis:	Abatacept is effective in lupus arthritis and this will be discernible in a small trial with robust endpoints which incorporates withdrawal of background immune suppressants
Study Schema: Drugs / Doses / Length of Treatment)	
 
1. Abatacept or placebo will be given in a 1:1 randomization subcutaneously q week for six months. Patients may elect to continue six more months on open label Abatacept.
 
2. Background Immune Suppressants will be withdrawn at any time between screening and the first dosing visit.
 
3. At or after screening, patients may elect 40-160 mg depomedrol shots prn not to exceed 320 mg total up to and including the Month 2 Visit (two months after the first dosing visit)
 
4. Additional steroids or immune suppressants, if necessary, will be allowed but the patient will be considered a non-responder on that basis
 
5. At the 3 month visit patients with significant clinical flare unresponsive to optional per protocol treatments may elect to receive open label Abatacept but will be considered non-responders in the primary endpoint at six months.
 

Study Objectives: 
 
• Primary:
 
• Secondary:
 
	
Primary Objective: To compare response rates between Abatacept-Treated and Placebo-Treated Patients with active lupus arthritis in a trial designed with background immune suppressant withdrawal, limited steroid rescue, and a robust, discriminatory endpoint. Statistical powering is based on this primary objective. The trial design and primary endpoint (response by BICLA) have been pre-tested by us for safety and ability to ensure placebo group non-response. This will support a rational decision about further development of abatacept for SLE at minimal cost.
 
2.) Secondary clinical endpoints will include: SRI 4/5, changes in joint counts, SLEDAI, BILAG, CLASI, PGA, and LFA simplified instrument measures. PK and immunogenicity studies will be performed to help in interpretation of outcomes. Novel biologic discovery will be integrated into the clinical trial to support both pre-specified and exploratory biomarker discovery. Data will be generated that might be used to help select more appropriate patient subsets for future trials and, along with PK data, help to guide optimal dosing strategies. Optimizing patient selection and dosing are important goals for further increasing demonstrable effect size in trials by increasing the response rates

	in the treatment group.
Study Design:	This study will be a double blind, randomized, placebo-controlled clinical trial with 1:1 randomization of patients to abatacept 125 mg weekly subcutaneous dose or placebo, with the withdrawal of background immune suppressants. Limited steroid rescue allowed per protocol. Additional meds will define non-response the primary endpoint date of six months. Flaring patients may elect to receive open label abatacept at Month 3 but will also be defined as non-responders in the primary endpoint. All patients may elect to receive open label abatacept for an additional six months after the primary endpoint date, with two follow up visits (2 and 4 months post withdrawal) to assess withdrawal effects and to complete the safety assessment.
Accrual Goal: (Total subjects)	This study will continue to recruit until we achieve the goal of 60 patients who complete study visits through the 6 month endpoint.
Accrual Rate: (Number of subjects expected per month)	We expect to enroll 5 patients/month given entry criteria, recruitment track record, and patient appeal of protocol (in particular the early crossover to open label treatment)
FPFV: LPFV: Follow Up:	
 
• FPFV: October 30 2013
 
• LPFV: December 31 2015
 
• Follow Up: April 31 2016
 

Correlative Studies: (PK/PD, etc.)	Extensive exploratory protocol-specific and ancillary immune pharmacodynamic studies, focusing first on changes in IFN alpha, BLyS and other B Cell pathways. A major focus will also be on T Cell pathways with a focus on T suppressor/TH17 dichotomy after treatment with abatacept. A responder analysis will be performed in order to generate hypotheses useful for selecting appropriate patients for this treatment and optimizing dosing strategies.
Inclusion Criteria:	
 
1) Signed Written Informed Consent
 
2) 4 1997 revised ACR Classification Criteria for SLE
 
3) Active polyarticular arthritis meeting at minimum BILAG 2004 B definition with a minimum of 3 tender and 3 swollen joints observed at the screening visit
 
4) Men and women 18 to 70 years of age.
 
5) Women of childbearing potential and men with partners of childbearing potential must use an acceptable method of birth control throughout the study
 
6) Women of childbearing potential must have a negative urine pregnancy test at screening and Study Day 1 (baseline visit) and may not be breast feeding
 

Exclusion Criteria:	
 
1) Current severe disease (e.g. acute nephritis appropriate for induction therapy, CNS lupus (excepting chorea, cranial neuropathy, and resolving optic neuritis) or any lupus condition requiring cyclophosphamide, biologic therapy, or IV bolus steroids of <math>\geq</math> 500 mg.
 
2) Subjects who are incapable of understanding or
 

	
completing study-related assessments.
 
3) Subjects with any condition, whether or not related to SLE, which, in the opinion of the investigator, might place a subject at unacceptable risk for participation in the study.
 
4) Subjects with a history of cancer in the last 5 years, other than non-melanoma skin cell cancers cured by local resection or carcinoma in situ.
 
5) Subjects who currently abuse drugs or alcohol.
 
6) Subjects with acute herpes zoster or cytomegalovirus (CMV) within 2 months of screening.
 
7) Subjects who have received any live vaccines within 3 months of first dose.
 
8) Subjects with any serious bacterial infection within the last 3 months, unless treated and resolved with antibiotics, or any chronic bacterial infection (eg, chronic pyelonephritis, osteomyelitis, or bronchiectasis).
 
9) Subjects at risk for tuberculosis (TB).
 
10) Subjects known to be positive for hepatitis B surface antigen or hepatitis C unless negative by PCR or RIBA
 
11) Acute hemolytic anemia with hemoglobin < 7.0 g/dL or known change in Hg by 2.0 g/dL within four months
 
12) WBC < 2500/mm^3 (< 3 x 10^9/L) unless due to chronic stable lupus activity
 
13) Platelets < 40,000/mm^3 (< 3 x 10^9/L) (If less than 100,000 must have been stable (within a range of 10,000/mm^3 ) within two months of screening or in two tests during the screening period.
 
14) Serum creatinine > 2 times the ULN
 
15) Serum ALT or AST > 2.5 times the ULN
 
16) Any other laboratory test results that, in the opinion of the investigator, might place a subject at unacceptable risk for participation in the study.
 
17) Known allergy/sensitivity to the study agent or carrier.
 
18) Treatment with investigational drug within 28 days (or 5 terminal half-lives) of the Day 1 dose.
 
19) Cyclophosphamide within 3 months of Day 1 or bolus IV steroids >/=500 mg within 1 month
 
20) Prednisone > 20 mg qd after the screening visit

Criteria for Evaluation: (Efficacy, safety, stopping rules, etc.)	
Efficacy: Primary endpoint will be response rates by “BICLA” (BILAG-based combined Lupus Assessment). Secondary efficacy endpoints will be the SRI (SLE Responder Index), changes in SLEDAI, BILAG, PGA, CLASI, DIAL and PRO endpoints. Safety: Adverse Events, Serious Adverse Events and Adverse Events of special interest (infusion reactions and infections) will be collected and described. Stopping Rules: Patients may be withdrawn by

	the investigator for non-compliance or safety. All patients terminating before six months will be considered non responders in the primary analysis. Use of off protocol immune suppressants will not necessarily dictate withdrawal but will determine non-responder status. A DSMB board will review data on a quarterly basis and may stop the study if needed.
Statistics:	
Primary Clinical Endpoint: proportion of patients on abatacept vs placebo who meet BICLA criteria at month 6 compared to baseline by Ch sq or Fishers Exact Test. Powering of the Study Based on the Primary Endpoint: Powering assumptions assume response rates ranging from 35-50%. based on data from patients with lupus arthritis in the Phase II abatacept study, where physicians rated 40% of the patients treated with abatacept as having “no flare.” Using the BICLA, response rates in the epratuzumab EMBLEM trial was also about 40% at optimal dosing, therefore this range seems applicable. Data from the BOLD study confirm that there should be a near zero (2.4%) percent response by BICLA at six months in the placebo group in a study with background IS withdrawal. Therefore our assumption of at least 5% response in the placebo group in an identical trial design is reasonable and with range of 40-50% response in the treatment group power > 0.8 to detect a difference. Exploratory Analysis of Primary Endpoint: To address potential confounders in a small study a propensity score will be applied to simplify multiple variables into one variable.
 
Secondary Clinical Endpoints: BICLA and SRI at each month. Mean SLEDAI, BILAG, CLASI, PGA, DIAL and PRO by paired T test. Main Biologic Endpoint: Patients who do or do not exhibit proposed relative differences in the ratio of IL6/IL23/IL17 to Foxp3/TGF<math>\beta</math> (suggesting T Cell signaling imbalance) or aberrant ErK phosphorylation (indicating abnormal signaling through B Cell receptor) at baseline will be compared for proportion of responders in treatment vs placebo group. Patients identified at baseline with high TH17 signal or ErK phosphorylation with <math>\geq</math> 50% change towards healthy mean (+2SD) after treatment will be compared separately for response rates. These endpoints will be described in terms of confidence intervals based on the primary clinical endpoint. Analysis of Secondary and Exploratory Biologic Endpoints will include mean (or median) change in cytokine, immunoglobulin and gene expression levels explored based on known patterns of overexpression in SLE. Bucketing of baseline profiles might be used to develop propensity scores suitable for a simplified refinement of the primary biologic endpoint by combining variables that might either increase or decrease the likelihood of response. Given the complex array of data we are likely to generate, principal component analysis can be applied to these exploratory studies to identify directions (principal components) along which the variation of the data is maximal.

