The study population will include patients between the ages of 18 and 70 who meet a minimum of 4 1997 revised ACR criteria for SLE and who present with a minimum of 3 tender and 3 swollen joints attributable to lupus arthritis. Patients may have other active manifestations of SLE, and, in the opinion of the investigator, they must be sick enough for intention to treat with a biologic and stable enough for this trial design, which includes withdrawal of any background immune suppressants, to be appropriate.

This study will enroll patients until 60 have completed the protocol through at least the six month point. Randomization will be 1:1 to abatacept or placebo. Approximately 30 patients are expected to complete each arm. At each visit history, physical, and blood tests appropriate to complete the outcome measures will be performed, and adverse event reporting and medication updates will be performed.

Subjects may continue to take nonsteroidal anti-inflammatory medications (including *prn* NSAIDS) and up to 20 mg prednisone (or oral steroid equivalent) daily during the study although steroids will be tapered as tolerated. If the patient is taking an immune suppressant (e.g. antimalarials, mycophenolate mofetil, azathioprine, leflunomide, methotrexate, a calcineurin inhibitor or belimumab) at screening, this must be stopped prior to or on the day of the baseline visit. Patients can elect to receive one or more depomedrol injection(s) up to a total of 320 mg total at the time of the screening visit and/or up to and including the Month 2 visit. Daily oral steroids will be tapered as tolerated if and when the patient begins to improve.

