Subjects will be encouraged to avoid off protocol medications if possible, but if off protocol medications are given, the patient may, at the discretion of the investigator continue in the protocol as a designated “non-responder”, and continue to be followed at monthly visits until the subjects reaches Month 6. Furthermore, patients may elect to receive open label abatacept as early as Month 3 (three Months after the first Dosing Visit) if their disease activity is not improved at that visit compared to baseline. Such subjects will also be designated as non-responders for the primary endpoint at Month 6. For those patients taking daily oral steroids at screening, they will be encouraged to taper these as tolerated if and when they begin to improve. Patients who withdraw from the protocol for any reason will be encouraged to come for safety follow up visits 2 and 4 months after the last study visit.

The primary endpoint will be determined at six months, but all patients can then choose to receive open label abatacept for an additional six months. Maximal duration of treatment will be 12 months. There will be two follow up visits two and four months after the end of study. However, patients who withdraw after six months will be considered completers of the primary study in the amassing of 60 completers. The criteria for evaluation will be improvement (without worsening) in signs, symptoms and diagnostic results as defined by the BICLA (primary endpoint). Additionally joint counts, the SRI 4/5, hybrid SLEDAI, BILAG 2004, CLASI, DIAL, Lupus PRO and SF-36 will be evaluated.

After receiving the first injection in clinic, patients will administer the study medication at home. Subjects will return to the clinic monthly for six months, and those who continue will be evaluated every 4 weeks for the second six months. There will be two follow up visits at two month intervals after the end of study for each patient. Visits at which maximal blood samples are taken due to PD scheduling are Screening, and Months 3, 6, 9 and 12 (up to 160 cc). At all other visits no more than 80 cc maximally can be drawn.

Please refer to the Time and Events Schedule for a grid of procedures.

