## 9. Statistical Considerations

**Enrollment is expected to include at least 70 screened and 60 randomized subjects** subjects have either reached a six month endpoint and/or been defined as a permanent non-responder for off protocol treatment or by dropping out of the protocol.

**The primary endpoint is the proportion of placebo vs treatment subjects who meet the primary endpoint of BICLA response using Chi Square analysis at month 6 as determined by an intent to treat analysis**

Subjects who drop out prematurely for any reason or are treated with off protocol medications or cross over to open label for lack of response at Month 3-6 are considered non responders at month 6.

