### 9.1 Sample Size Determination

**Sample Size** Based on data from the BOLD study confirming the low response rates in a placebo group at 6 months in a study design identical to the structure of this protocol (1/41 patients or 2.4% met the BICLA response at 6 months in that study) and based on the assumption that the response rate to abatacept using this design and these endpoints would be at least equivalent to what was found in the Phase II Epratuzumab or Phase III BLISS studies (roughly 40-50% response). The sample size was optimized at 60 patients in a 1:1 randomization scheme with alpha = 0.5 and desired power 0.8.

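### Do the two descriptions of the 60-patient target, and the loose use of completing Month 6, leave the sample size or the primary analysis set open?

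*Combined protocol and SAP*

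**What the plan says.** The Synopsis (Accrual Goal) says: "This study will continue to recruit until we achieve the goal of 60 patients who complete study visits through the 6 month endpoint". Section 4.1 repeats the rule: "This study will enroll patients until 60 have completed the protocol through at least the six month point". It adds "Approximately 30 patients are expected to complete each arm" and explains how later leavers count: "patients who withdraw after six months will be considered completers of the primary study in the amassing of 60 completers".

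Section 9 opens differently: "Enrollment is expected to include at least 70 screened and 60 randomized subjects". A clause without its opening words follows: "subjects have either reached a six month endpoint and/or been defined as a permanent non-responder for off protocol treatment or by dropping out". Section 9.1 says "The sample size was optimized at 60 patients in a 1:1 randomization scheme", without saying whether these are randomised or completing patients.

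On the analysis, Section 9 makes the primary comparison "BICLA response using Chi Square analysis at month 6 as determined by an intent to treat analysis". It then counts anyone who drops out, takes off-protocol medication or crosses to open label as a non-responder at Month 6. The Synopsis (Criteria for Evaluation) treats early termination the same way. Section 4.2.3 calls patients evaluable for the primary endpoint if they complete Month 6, and its next sentence makes those lost before Month 6 non-responders. Section 9.3.1 describes testing efficacy in patients who complete the protocol. Section 9.2, despite its title on analysis populations, gives eligibility and power and defines no analysis set.

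**The concern.** A patient who leaves at Month 2 and stops attending counts towards the 60 under the Section 9 clause, but not under the Synopsis or Section 4.1. Followed literally, the two rules stop recruitment at different points, and Section 9.1 does not say which one the power table assumes. If 60 means randomised and the planning rates describe completers, counting dropouts as failures would lower both response rates and reduce power.

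The second worry is the denominator. The evaluable sentence in 4.2.3 and the wording of 9.3.1 could be read as licence to drop early leavers from the primary comparison. In a trial of this size that could change the estimated difference, and it would give up the protection of analysing patients as randomised.

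**Working it through.** **1. Denominator, by comparing the text.** Three places make early leavers non-responders: the Synopsis (Criteria for Evaluation), Section 4.2.3 and the opening of Section 9. Section 9 also names intent to treat. The evaluable sentence in 4.2.3 is qualified at once by the sentence after it. Section 9.3.1 is narrative about how the endpoint addresses the hypothesis; it sets no exclusion. Nowhere is a completers-only primary analysis instructed. The Time and Events Schedule puts randomisation and first dosing at the same visit, so there is little room for a randomised-but-untreated group either.

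**2. Accrual, by comparing the text.** The first part of the Section 9 sentence is a minimum. Randomising 64, 67 or 75 patients to obtain 60 completers satisfies it. Only the damaged clause after it pulls the other way. Patients who stop drug or take other treatment but keep attending visits count under both rules, so the rules differ only for patients who miss Month 6.

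**3. The plan's power figure.** Inputs: 30 per arm (60 patients, 1:1, Sections 9.1 and 9.2); alpha 0.05 (Section 9.2 and the power table), taken as two-sided; 40% against 5% (power table, stated power 0.86). The continuity-corrected normal approximation is

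power = Φ{ [ (p1 − p2 − 1/n)√n − 1.96√(2p̄(1 − p̄)) ] / √(p1(1 − p1) + p2(1 − p2)) }.

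With n = 30 and p̄ = 0.225:
- (0.35 − 0.0333) × 5.477 = 1.734
- 1.96 × √0.34875 = 1.157
- denominator √0.2875 = 0.536
- (1.734 − 1.157)/0.536 = 1.076, so power = 0.859, matching 0.86

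Over the table's seven columns the formula gives 0.848, 0.869, 0.897, 0.804, 0.859, 0.749 and 0.830, against the stated 0.84, 0.86, 0.89, 0.80, 0.86, 0.77 and 0.84. For the 40% against 5% column, exact power is 0.893 for Fisher and 0.943 for uncorrected chi-square.

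**4. Size of the accrual difference.** The documents give no rate for missing Month 6, so d = 5%, 10% and 20%, equal in both arms, are assumptions. Randomised number for 60 completers = 60/(1 − d), rounded up: 60/0.95 = 63.2, so 64; 60/0.90 = 66.7, so 67; 60/0.80 = 75. The excess over 60 is 4, 7 and 15.

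**5. Power under each reading, 40% against 5%.** The table takes the harshest premise: the planning rates hold only in completers, and everyone missing Month 6 is a non-responder, so both rates are multiplied by (1 − d). Entries are continuity-corrected / exact Fisher / exact uncorrected chi-square.

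| d | 60 completers, all randomised analysed | Exactly 60 randomised |
|---|---|---|
| 5% | 0.858 / 0.897 / 0.945 (64) | 0.828 / 0.866 / 0.929 |
| 10% | 0.847 / 0.900 / 0.943 (67) | 0.794 / 0.835 / 0.912 |
| 20% | 0.831 / 0.892 / 0.937 (75) | 0.714 / 0.753 / 0.871 |

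If the planning rates already count dropouts as failures, exactly 60 randomised stays at 0.859 / 0.893 / 0.943 whatever d is.

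**6. Which premise the documents support.** The 40% is described as a share of patients treated with abatacept in the earlier Phase II study, and the 2.4% as 1 of 41 patients in the prior study. Neither is described as a rate among completers.

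**The case for a change.** The best case for a change is that the conflict needs no assumption to see: the damaged clause in Section 9 names dropouts among those counted, and the completer rule excludes them. If early leavers are non-responders, everyone randomised is evaluable, so the evaluable sentence does no work. Section 4.2.3 adds another meaning of completing the protocol (Month 6 plus two follow-up visits), and Section 9.2 is where a reader would look for the answer. A spread of 4 to 15 patients is 7% to 25% of 60. The 45% against 10% column has no slack: under the harsh premise at 10% missing, its continuity-corrected power falls from 0.804 to 0.729 with exactly 60 randomised, and to 0.788 with 60 completers.

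The wording part of this stands. The consequence does not. The completer target appears in the Synopsis and twice in Section 4.1, and Section 4.1 says that those who leave after six months still count, which settles what completing means for accrual. The power losses rest on the completer-rate premise together with an invented dropout rate, and the larger ones also need recruitment to stop at exactly 60 randomised, although Section 9 says at least 60. At 10% missing in the 40% against 5% case, only the normal approximation falls below 0.8 (0.794); exact Fisher is 0.835. Nor does either stopping rule threaten type I error: both work on a count pooled over blinded arms, not on the treatment comparison.

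**Conclusion.** No change to the plan follows. The accrual mismatch is a clerical slip in one damaged sentence, set against a target stated consistently in the Synopsis and Section 4.1. The missing formal definition in Section 9.2 is a gap an analyst would fill the same way every time: all randomised patients, with anyone lacking a Month 6 result counted as a non-responder, because the rest of the plan says so.

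The practical difference is 4, 7 or 15 randomised patients at an assumed 5%, 10% or 20% missing Month 6. For 40% against 5%, continuity-corrected power is 0.83 to 0.86 when recruiting to 60 completers, even on the least favourable premise about the planning rates. It is 0.86 with 60 randomised if those rates already include dropouts as failures. Exactly 60 randomised with completer-only rates would give 0.83, 0.79 or 0.71, but the documents do not support that combination. Tidier wording would help a reader, but it would not alter who is analysed, how they are classified or the test used.

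This conclusion assumes a two-sided 0.05 level and equal dropout in both arms.
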